## 4.2 PARTICIPANT DISPOSITIONS

The number (%) of participants included in each of the analysis populations listed in [Table 5](#) will be summarized. Reasons for exclusion from the population without trial impact (disruption) due to COVID-19 will be summarized.

Pre-screen failures are defined as participants who consent to participate in the pre-screening phase of the study but are not subsequently screened. The number (%) of pre-screen failures and reasons for pre-screen failures will be provided in the pre-screened population.

Screen failures are defined as participants who consent to participate in the study but are not subsequently enrolled. The number (%) of screen failures and reasons for screen failures will be provided in the screened population.

Regarding study intervention discontinuation, the following definitions will be used:

- Permanent **partial** study intervention discontinuation is defined as the discontinuation of at least one of the study drugs but at least one is continued.
- Permanent **full** study intervention discontinuation is defined as the discontinuation of all the study drugs.

The number (%) of participants in the following categories will be provided:

- Enrolled participants
- Enrolled but not treated participants
- Enrolled and treated participants
- Participants still on study intervention
- Participants who discontinued the study intervention and main reason for permanent full study intervention discontinuation
- Participants who discontinued the study intervention and main reason for permanent partial discontinuation of tusamitamab ravtansine
- Participants who discontinued the study intervention and main reason for permanent partial discontinuation of ramucirumab
- Participants who discontinued the study and main reason for study discontinuation

Reasons for permanent full/partial study intervention discontinuation and study discontinuation such as “adverse event” and “other reasons” will be split as related or not related to COVID-19 (if applicable).

The number (%) of treated and not enrolled participants will also be summarized.

In addition, the number (%) of participants prescreened, prescreen failed, screened, screen-failed, enrolled, enrolled and treated, with permanent full study intervention discontinuation, and with study discontinuation will be provided by country and site.

For all categories of participants (except for the prescreened, screened, not enrolled categories) percentages will be calculated using the number of participants in the all-treated population as the denominator.

### Protocol deviations

Critical and major protocol deviations (automatic or manual) will be summarized in the all-treated population as well as displayed separately as related or not related to COVID-19 (if applicable).

## **4.3 PRIMARY ENDPOINTS ANALYSIS I**

As it is a two-part study, there are 2 primary endpoints: study-drug related dose-limiting toxicity at Cycle 1 and Cycle 2 in Part 1, and confirmed objective response as per RECIST 1.1 in Part 2.

### **4.3.1 Definition of endpoints**

#### ***4.3.1.1 Study-drug related DLT at Cycle 1 and Cycle 2***

The primary safety endpoint is studydrug-related DLT in Part 1 at Cycle 1 and Cycle 2 (from C1D1 to C2D14). The list of DLTs to be considered of the study is defined in the protocol (see Table 4 of the study protocol). For analysis purposes, DLTs will be identified based on the AEs reported on the e-CRF DLT page during the DLT observation period in Part 1.

#### ***4.3.1.2 Confirmed objective response***

The primary efficacy endpoint is confirmed objective response determined according to RECIST 1.1. A confirmed objective response is defined as a confirmed CR or PR as best overall response.

The BOR will be derived according to RECIST 1.1 definitions (1, 2) based on the investigator's assessment. The BOR is the best overall response observed from the date of the first administration of IMP until documented disease progression, death, start of an anticancer therapy, or analysis cut-off date, whichever occurs first.

### **4.3.2 Main analytical approach**

#### ***4.3.2.1 Study-drug related DLT at Cycle 1 and Cycle 2***

The primary safety analysis is based on the primary estimand 1 introduced in Section 1.2.1. It is defined according to the following attributes:

- The endpoint is study-drug related DLT during the DLT observation period, ie, Cycle 1 and Cycle 2, from Cycle 1 Day 1 to Cycle 2 Day 14.
- The treatment condition of interest is tusamitamab ravtansine in combination with ramucirumab, by dose level (if applicable).

- The analysis population is the DLT-evaluable population (defined in [Section 3](#)).
- No intercurrent events handling strategy is defined due to the definition of the analysis population. Indeed, participants from the DLT-evaluable population will not experience any anticipated intercurrent event (study intervention discontinuation, study discontinuation, start of an anticancer therapy, or death) before experiencing a DLT at Cycle 1 or Cycle 2, or before completing the Cycle 2, whichever is earlier.
- The population-level summary will include the incidence of DLTs at Cycle 1 and Cycle 2, defined as number and percentage of participants experiencing at least one study-drug related DLT. There will be no missing data in the analysis population.

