Part 1 (Safety Run-In): In Part 1, participants will be treated with tusamitamab ravidansine and ramucirumab to assess the tolerability of the combination to be used in the subsequent part of the study. The first 3 participants will receive ramucirumab at 8 mg/kg followed by tusamitamab ravidansine at 100 mg/m^2 every 2 weeks (Q2W). Administration of tusamitamab ravidansine will begin at least 1 hour after completion of ramucirumab infusion.

The DLT observation period is the first 2 cycles (approximately 28 days). A DLT-evaluable participant must have completed 2 cycles of treatment or have been discontinued from study treatment because of a DLT; DLT non-evaluable participants will be replaced.

A minimum delay of 1 week is required between the initial dose in the first participant treated in a DL cohort and dosing the next 2 participants treated at the same DL.

- If $\leq 1/3$ participants treated at the starting dose experiences a DLT, 3 additional participants will be treated to confirm the tolerability of the combination.
 - If $\leq 1/6$ participants treated at the starting dose experiences a DLT, the starting dose will be the RP2D.
 - If $\geq 2/6$ participants treated at the starting dose experience DLTs, the dose will be de-escalated to DL -1.
- If $\geq 2/3$ participants treated at the starting dose experience DLTs, the dose will be de-escalated to DL minus 1 (DL -1).
- If ≤ 1 of the first 3 participants treated at DL -1 experiences a DLT, 3 additional participants will be treated at this DL.
 - If $\leq 1/6$ participants treated at DL -1 experiences a DLT, DL-1 will be the RP2D.
 - If $\geq 2/6$ participants treated at DL -1 experience a DLT, an alternative dosage might be considered or the doublet cohort may be stopped.
- If $\geq 2/3$ participants treated at DL -1 experience a DLT, an alternative dosage might be considered or the doublet cohort may be stopped.

Note: if $\geq 2/6$ or $\geq 2/3$ participants treated at DL -1 experience DLTs, an alternative dosage might be considered from a safety viewpoint by the Sponsor after consulting with SC. Dose reduction is shown in [Table 4](#).

Table 4 - Dose reduction for the doublet cohort Part 1 (safety run-in)

[figure not shown]
Dose level (DL)	tusamitamab rfvansine	Ramucirumab
Starting dose	100 mg/m ² Q2W	8 mg/kg Q2W
Minus -1 (DL-1)	80 mg/m ² Q2W	8 mg/kg Q2W

DL=dose level; Q2W=every 2 weeks.

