9.2.1 Sample size for the doublet cohort, safety run-in (Part 1)

The actual sample size is expected to vary depending on DLTs observed. It is anticipated that around 6 to 12 DLT-evaluable participants will be enrolled in the safety run-in part of the cohort.

9.2.2 Sample size for the doublet cohort, Part 2

The initial plan is to treat a total of 30 participants evaluable (at least one post-baseline tumor assessment) for activity. The 6 participants treated at the recommended dose level in the safety run-in part will also be evaluable for this second part of the cohort.

Estimated ORR and 95% exact CI by numbers of responders from a sample size of 30 participants evaluable for activity are summarized in [Table 14](#).

Table 14 - Estimated objective response rate (ORR) depending on number of responders

Number of Responders (N=30)	Objective Response Rate in % (95% Clopper-Pearson CI)
6	20.00% (7.71% - 38.57%)
8	26.67% (12.28% - 45.89%)
9	30.00% (14.73% - 49.40%)
11	36.67% (19.93% - 56.14%)
12	40.00% (22.66% - 59.40%)

CI=confidence interval.

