9.4.2.1 Analysis of primary safety endpoint

Dose-limiting toxicities observed during the DLT observation period (Cycle 1 and Cycle 2 for the doublet cohort; Cycle 1 for the triplet cohort) will be summarized on the DLT-evaluable population, by dose level. In addition, AEs that meet the DLT criteria in subsequent cycles will be summarized on the all-treated population. Details will be provided by patient.

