## 2 SAMPLE SIZE DETERMINATION

The safety run-in part aims to establish the RP2D of tusamitamab ravtansine in combination with ramucirumab according to DLTs observed.

Part 2 of this study is designed to obtain preliminary efficacy, safety, and PK data on tusamitamab ravtansine administered in combination with ramucirumab to participants with NSQ NSCLC. As the second part is not intended to explicitly test a hypothesis, calculations of power and Type I error were not considered in the study design.

Assuming a pre-screening failure rate of 80% and a study screening failure rate of 20%, approximately 225 participants will be pre-screened to achieve a total of up to approximately 36 treated participants, including Part 1 (safety run-in) and Part 2 of the study.

Sample size of the safety run-in part:

The actual sample size is expected to vary depending on DLTs observed. It is anticipated that around 6 to 12 DLT-evaluable participants (as defined in Section 3) will be enrolled in the safety run-in part of the study.

Sample size of Part 2:

The initial plan is to treat a total of 30 participants evaluable for activity (ie, having at least one post-baseline evaluable tumor assessment, early clinical progression, or death due to disease progression). The 6 participants treated at the RP2D in the safety run-in part will also be evaluable for this second part of the study.

Estimated ORR and 95% exact CIs by number of responders from a sample size of 30 participants evaluable for activity are summarized in Table 4.

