In practice, a participant will be included in the DLT-evaluable population (applicable to Part 1 only) if a “Dose Limiting Toxicities” e-CRF page has been filled in at the end of Cycle 1 and at the end of Cycle 2 (or Cycle 1 only if participant did not receive Cycle 2 because of a DLT). This includes participants followed up to the end of the DLT observation period or participants having experienced a DLT before the end of the DLT observation period and validated by the Study Committee. Participants with an overdose (defined as a dose received at least 30% above the intended dose) of tusamitamab ravtansine or ramucirumab at any of the two first infusions will be excluded from the DLT-evaluable population.

Participants treated with study intervention before or without being enrolled will not be considered enrolled and will not be included in any analysis population. The safety experience of these participants will be reported separately.

Enrolled participants for whom it is unclear whether they took the study intervention will be considered as treated and will be included in the all-treated population.

For any participant enrolled more than once, only the data associated with the first enrollment will be used in any analysis population. The safety experience associated with any later enrollment will be reported separately.

In practice, participants whose BOR is nonevaluable due to minimum criteria for SD duration not met (ie, overall response of SD and the minimum duration, defined as  $0.75 \times$  duration between the first IMP intake and the first planned tumor assessment is not met) and there is no subsequent evaluable tumor assessment, or documented PD after two or more nonevaluable tumor assessments (ie, overall response of PD and the time between the date of first IMP intake and the documentation of PD is greater than the theoretical planned date of the second tumor assessment) will be considered as not evaluable for the activity population.

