## 4 STATISTICAL ANALYSES

### 4.1 GENERAL CONSIDERATIONS

This study is not intended to explicitly test a hypothesis. 95% confidence intervals will be provided for primary and secondary efficacy endpoints.

All efficacy endpoints based on radiological assessments of tumor burden (ie, confirmed objective response, PFS and DOR) will be derived using the local radiologist's/Investigator's assessment.

In general, continuous data will be summarized using the number of observations available, mean, standard deviation (SD), median, Q1, Q3, minimum, and maximum. Categorical and ordinal data will be summarized using the count and percentage of participants.

The baseline value is defined as the last available value before the first dose of IMP.

The study cut-off for analysis of the primary efficacy endpoint, ORR, corresponds to the date on which all evaluable treated participants have had at least 2 post-baseline tumor assessments, experienced confirmed objective response, or have discontinued the study for any reason, up to approximately 6 months (4 months for 2 tumor assessments and 2 months for confirmation of response, if needed) from the date of the last participant's first IMP administration.

The analysis cut-off date is defined as the date of the database extraction that will be performed for the analysis.

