**Table 10 - Selections for AESIs and other AEs of interest**

AESIs and other AEs of interest	Selection
AESIs	eCRF AESI specific tick box on the AE page
DLT during DLT observation period	eCRF specific DLT page
Other AEs of interest	
Any AE meeting DLT criteria beyond the DLT observation period	AEs reported on the eCRF DLT page outside the DLT observation period
Corneal events	CMQ "Corneal events compound level" containing the PTs included in both SOC "Eye disorders" and SMQ "Corneal disorders" (Narrow)

AESIs and other AEs of interest	Selection
Ocular/visual symptoms (excluding corneal disorders)	CMQ "Eye disorders exclude corneal disorders" containing PTs included in SOC "Eyes disorders" and excluding PTs in SMQ "Corneal disorders" (Narrow)
Cardiac conduction defects	SMQ "Conduction defects" (Narrow)
Peripheral neuropathy events	SMQ "Peripheral neuropathy" (Narrow and Broad)
Colitis events (excluding infective)	CMQ "Colitis (excluding infective)" containing PTs included in HLT "Colitis (excl infective)"
Hypersensitivity events	SMQ "Hypersensitivity" (Narrow) and adverse event occurring on the day or the day after the infusion
Hepatic disorders adverse events	SMQ "Hepatic Disorders" (Narrow and Broad)
Hematological adverse events	SMQ "Haematopoietic cytopenias" (Narrow and Broad)
AE related to COVID-19 illness	SMQ "COVID-19" (Narrow)

An overview of corneal TEAE will be provided with the following AE categories: any corneal TEAE, Grade  $\geq 3$  corneal TEAE, treatment-emergent corneal SAE, corneal TEAE leading to permanent full study intervention discontinuation, corneal TEAE leading to permanent partial discontinuation of tusamitamab ravtansine, corneal TEAE related to IMP, Grade  $\geq 3$  corneal TEAE related to IMP, and corneal TEAE leading to dose modification of tusamitamab ravtansine (cycle delay, dose omission, or dose reduction).

In addition, a summary table of corneal events will be displayed by grade.

A summary of treatment-emergent corneal events will be provided.

- Number (%) of participants by worst grade.
- Cycle of first onset of corneal event regardless of the grade.
- Cycle of first onset of corneal event with the worst grade.
- Relationship to the study intervention: in case of multiple events with different relationships, if any event is related, then the relationship will be considered as related.

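### The doublet's primary DLT incidence is reported as x/6 without an interval, and Cycle 1-2 DLT-criteria events in the roughly 24 Part 2 participants at the RP2D probably enter neither DLT summary

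*SAP*

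**What the plan says.** **Decision rule.** Under Protocol Section 4.1, when at most 1/6 "participants treated at the starting dose experiences a DLT, the starting dose will be the RP2D". SAP Section 2 plans the run-in size: "It is anticipated that around 6 to 12 DLT-evaluable participants".

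**Primary DLT analysis.** SAP Section 4.3.2.1: "The population-level summary will include the incidence of DLTs at Cycle 1 and Cycle 2, defined as number and percentage of participants experiencing at least" (a single DLT). SAP Section 4.1 gives intervals to efficacy only: "95% confidence intervals will be provided for primary and secondary efficacy endpoints".

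**Who is in it.** SAP Section 3, below Table 5, opens its working rule with "In practice, a participant will be included in the DLT-evaluable population (applicable to Part 1 only"). SAP Section 4.3.1.1 likewise identifies DLTs from the DLT page during the Part 1 observation period. The doublet's DLT-evaluable definition in Protocol Section 9.3 (Table 15) has no Part 1 limit, although Protocol Table 3 makes DLT incidence a Part 1 endpoint.

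**Second summary.** Protocol Section 9.4.2.1: "In addition, AEs that meet the DLT criteria in subsequent cycles will be summarized on the all-treated population". SAP Table 10 selects "AEs reported on the eCRF DLT page outside the DLT observation period".

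**Part 2 size.** Protocol Section 9.2.2: "The initial plan is to treat a total of 30 participants evaluable" for activity. The six run-in participants treated at the recommended dose are counted among the 30.

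**The concern.** The first primary objective is to assess tolerability and confirm the dose. As planned, the answer is a fraction out of six with no statement of its uncertainty. The other primary endpoint, ORR, gets a Clopper-Pearson interval and a precision table.

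The trial will treat about five times as many participants at the RP2D as it counts for DLTs. It observes all of them through Cycles 1 and 2, but the rules for the two DLT summaries appear to leave a gap. A Part 2 participant is outside the SAP's DLT-evaluable population, and Cycle 1 or 2 is not a subsequent cycle. A Grade 3 keratopathy in Cycle 2 of Part 2 would then be in neither summary, while the same event in Cycle 3 would be in the second. At stake is a table of DLT-criteria events that omits the first 28 days of about 80% of participants at the RP2D, and so undercounts.

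**Working it through.** **1. The plan's own figures.** Exact Clopper-Pearson limits at N=30 reproduce SAP Table 4: 6/30 gives 7.71% to 38.57% and 12/30 gives 22.66% to 59.40% (all five rows agree). The documents give no precision figure for the DLT endpoint.

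**2. Interval for the run-in result, same method.**
- 0/6: upper limit 1 − 0.025^(1/6) = 45.9%, so 0 to 45.9%.
- 1/6: 0.4% to 64.1%.

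**3. Participants affected.** 30 planned − 6 from the run-in = 24 treated only in Part 2, and 24/30 = 80%. This assumes that the RP2D group is 6 + 24.

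**4. Where one event goes.** Take a Table 5 event at the RP2D, under the SAP's Part 1 restriction.

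| Participant and timing | Primary DLT summary | Second summary, protocol wording | Second summary, SAP Table 10 |
|---|---|---|---|
| Part 1 (DLT-evaluable), Cycle 1-2 | Counted | No | No |
| Part 1, Cycle 3 or later | No | Counted | Counted |
| Part 2, Cycle 1-2 | No | No | Depends on reading |
| Part 2, Cycle 3 or later | No | Counted | Counted |

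The Table 10 entry turns on whether the DLT observation period exists for a Part 2 participant. If the period means Cycles 1 and 2, the event is inside it and is not selected. If the period exists only in Part 1, the event is outside it and is selected, provided that sites complete the DLT page in Part 2, which neither document states. The protocol's reference to later cycles favours the first reading.

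Under Protocol Table 15 taken literally, Part 2 participants with two adequately dosed cycles would enter the DLT-evaluable population itself. Two programmers could therefore produce different denominators for a primary endpoint.

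**5. Context: the at-most-1/6 rule.** With independent participants and true DLT rate p, P(pass) = (1−p)^6 + 6p(1−p)^5. Any path ending at 1/6 or fewer also has at most 1/3 at the first look, so staging does not change this.

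| Assumed p | P(pass) |
|---|---|
| 20% | 0.262 + 0.393 = 66% |
| 25% | 0.178 + 0.356 = 53% |
| 33% | 0.088 + 0.263 = 35% |
| 50% | 0.016 + 0.094 = 11% |

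These rates are assumptions. The documents name no unacceptable DLT rate.

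**6. What a pooled estimate adds.** If all 30 are assessable for Cycles 1-2, 3/30 gives 2.1% to 26.5% and 5/30 gives 5.6% to 34.7%. Given that Part 1 was passed, the chance of at least 6/30 overall is 5% at p = 10%, 46% at 20%, 69% at 25% and 92% at 33%.

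**The case against.** **The events are not hidden.** This is correct and limits the point. Safety tables use all treated participants, so Part 2 Cycles 1-2 are included. Corneal events have analyses of their own: worst grade, cycle of first onset and Kaplan-Meier time to onset (SAP Section 4.7.2). Haematological events, graded laboratory abnormalities and 24-hour urine protein are also covered. Grade 3 or higher keratopathy and every protocol-defined DLT are AESIs (Protocol Section 8.3.1). A reader might infer that early toxicity at the RP2D is never looked at again; the documents do not support that. None of these tables gives one Cycle 1-2 rate of Table 5 events, and that is all that is missing.

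**The exclusion is a matter of wording.** This stands in part. Table 10 can be read to take the Part 2 events, and Protocol Table 15 has no Part 1 limit. That ambiguity is itself a reason to settle the text.

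**The 35% pass probability condemns the run-in.** A reader might infer this, but one third is an assumed benchmark and the figure belongs to a rule that the fix leaves alone. Safety analysis here is descriptive, with no test to which power could apply.

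**A pooled count would tell good doses from bad.** Only at the extremes. At a cut-off of 6/30 it separates 10% from 33% but not the rates between.

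**Part 2 events are not the same quantity.** This stands. The Study Committee confirms DLTs and, in the doublet, meets regularly only during Part 1 (Protocol Section 10.1.5). Primary G-CSF prophylaxis is barred only in Part 1 (Protocol Section 6.5.1). The Table 5 item for any other event judged dose limiting cannot be derived from adverse event data.

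**Anyone can compute an interval from x/6.** True, but the plan already reports such an interval for its other primary endpoint.

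**Conclusion.** The point holds as a reporting gap that is cheap to close. The Part 1 DLT incidence has no interval, although the exact one reaches 45.9% at 0/6 and 64.1% at 1/6. On the protocol's wording and the likelier reading of SAP Table 10, Cycle 1-2 DLT-criteria events in about 24 of 30 participants at the RP2D enter neither DLT summary. The count of 24 assumes that the planned numbers are met, and the exclusion assumes that the SAP's Part 1 restriction governs.

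The point does not extend to a claim that safety at the RP2D goes unchecked or that the run-in rule is wrong. A pooled estimate narrows the uncertainty, with about five times the participants, but is not a pass/fail test. With no acceptable limit stated in the documents, the tolerability conclusion should not be tied to its upper bound.

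**What to change.** 1. **Close the gap.** In SAP Table 10 and Protocol Section 9.4.2.1, define the all-treated summary as any event meeting DLT criteria that the Part 1 DLT analysis does not count, including Cycles 1-2 in Part 2. Reconcile the doublet's DLT-evaluable definition in Protocol Section 9.3 with the SAP's Part 1 restriction. The cross-reference in SAP Section 4.3.1.1 also needs correcting: it cites protocol Table 4, but the DLT list is now Table 5.
2. **Add a supplementary descriptive estimate.** Among all participants treated at the RP2D (Part 1 and Part 2), report the proportion with an event meeting the objective Table 5 criteria in Cycles 1-2, with a Clopper-Pearson 95% interval. Label it *DLT-criteria events*, not confirmed DLTs. Show the neutropenia criteria separately because of the G-CSF difference.
3. **Add a Clopper-Pearson 95% interval** to the Part 1 DLT incidence by dose level in SAP Section 4.3.2.1.

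The run-in decision rule is unchanged. Any triplet interval belongs in the protocol or a triplet SAP, because this SAP excludes that cohort (Section 1.1).

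**Cost:** wording, one table and two intervals, with no added participants or visits. Graded adverse events, weekly haematology in Cycles 1-2 and urinalysis every cycle are already collected. If the DLT page was not completed in Part 2, events must be derived from adverse event and laboratory data. Part 2 events will lack routine Study Committee confirmation, the judgement-based Table 5 item is left out, and the Part 1 interval will be visibly wide.
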